19.7. Stopping Rules

Not applicable.

20. Study Monitoring, Auditing and Inspecting

20.1. Study Monitoring Plan

20.1.1. Quality Assurance and Quality Control

The principal investigator will be monitoring the conduct of the study throughout, data will be reviewed at 50% recruitment and 100% recruitment.

20.1.2. Safety Monitoring

Adverse events will be identified and recorded on each subject form by the monitor and will be reviewed by the primary investigator who is present during all procedures.

The **Principal Investigator** will confirm that all adverse events (AE) are correctly entered into the AE case report forms by the coordinator; be available to answer any questions that the coordinators may have concerning AEs; and will notify the IRB and/or DSMB of all applicable AEs as appropriate. All assessments of AEs will be made by a licensed medical professional who is an investigator on the research.

21. Future Undetermined Research: Data and Specimen Banking

21.1. Data and/or specimens being stored

Not Applicable. No specimens will be collected, and data will not be stored once this study is completed.

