2.3. Study Rationale

While the procedures of flexible bronchoscopy and endobronchial ultrasound is commonly performed to assess a wide range of lung disease, studies evaluating the mode of administration of topical lidocaine to prevent coughing and improve efficiency of the procedure have not yet been completed. We propose a prospective, randomized, stratified sampling, open label study of topical vs nebulized vs atomized lidocaine during flexible bronchoscopy and endobronchial ultrasound. Postoperative outcome assessors will be blinded to intraoperative therapy. We propose to evaluate the different modes of administration of topical lidocaine and their effect on the number of severe coughs as per anesthesia and the bronchoscopist, total dosing of anesthesia, post-procedure cough and sore throat and complications related to lidocaine.

As there have been no studies in regards to the mode of lidocaine application in bronchoscopy, our study is a feasability study to identify if a difference is present between nebulized and topical groups. If one is identified, we will plan to determine number needed to power a future superiority study.

Inclusion and Exclusion Criteria

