- 2. Nebulizer 2 % (preservative free) lidocaine (dose 2mg/kg max dose 160 mg) will be administered via a jet nebulizer, in the operating room over ten minutes, followed by procedure immediately after. The patient will be sitting propped up and his SpO2, EKG and BP will be monitored during this time. The jet nebulizer supply tube will be connected to central oxygen at 6 L/min and the duration of nebulization will be dryness of the nebulizing chamber or max of 10 minutes. [The Salter Series Small Volume Jet Nebulizer will be used.]
- 3. Vibrating Mesh Nebulizer 2 % (preservative free) lidocaine (dose 2mg/kg max dose 160 mg) will be administered via a vibrating mesh nebulizer, in the operating room over ten minutes, followed by procedure immediately after. The patient will be sitting propped up and his SpO2, EKG and BP will be monitored during this time. The jet nebulizer will be

connected to central oxygen at 6 L/min and the duration of nebulization will be dryness of the nebulizing chamber or max of 10 minutes. [The Aerogen Solo Vibrating Mesh Nebulizer will be used.]

Patient will undergo scheduled procedure of flexible bronchoscopy or endobronchial ultrasound examination. During procedure, bronchoscopist and anesthesiologist will count the number of episodes of cough. Cough is defined as a cough which requires intervention such as additional dose of anesthetic or requires a pause in the procedure. During procedure, BIS monitor average, number of vasopressor interventions for MAP <60, induction time, procedure time and wake up time will be documented in the research record.

Following procedure, patient will be brought to post-op anesthesia care unit. Time to discharge readiness will be collected as well as the responses of the patient to the following questions:

- sore throat: absent, mild, moderate, severe
- cough: absent, mild, moderate, severe

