8.1. Number of Subjects

48 patients randomly assigned to lidocaine application technique (24 in topical, 12 in jet nebulizer and 12 in vibrating mesh nebulizer). Among each group there will be stratification of flexible bronchoscopy/endobronchial ultrasound procedures and inpatient/outpatient.

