8.3. Statistical methods

Descriptive statistics will be used for continuous variables, and presented as medians and interquartile ranges. Categorical variables will be expressed as percentages. The estimated sample size within our institution is 48 patients.

9. Confidentiality, Privacy and Data Management

See Research Data Plan Review Form.

10. Data and Safety Monitoring Plan

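### The median and IQR planned for the severe-cough count are too coarse to size the follow-on trial, and section 21.1, read literally, rules out re-deriving that size later

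*Combined protocol and SAP*

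**What the plan says.** - **Purpose.** Section 2.3 calls this a feasibility study that looks for a difference between nebulized and topical lidocaine. The next step is conditional: "If one is identified, we will plan to determine number needed to power a future superiority study". No endpoint scale, error rate, power, method or date is given for that calculation.
- **Outcome.** Under section 7.1, "bronchoscopist and anesthesiologist will count the number of episodes of cough". An episode counts if it leads to a pause or to an added dose of anesthetic.
- **Summaries.** Section 8.3: "Descriptive statistics will be used for continuous variables, and presented as medians and interquartile ranges", and "Categorical variables will be expressed as percentages". Section 10.7 repeats both. Neither names a mean, a variance, a frequency table or an any-versus-none percentage for the cough count.
- **Size.** Section 8.1 gives "24 in topical, 12 in jet nebulizer and 12 in vibrating mesh nebulizer". Section 8.2 marks sample size determination as not applicable.
- **Data after the study.** Section 21, on banking for undetermined future research, says in 21.1: "No specimens will be collected, and data will not be stored once this study is completed". Section 21.3 gives storage duration as not applicable. Section 9 refers data management to a Research Data Plan Review Form that is not part of the document.

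**The concern.** A later trial that compares cough counts needs a mean and a dispersion, or the proportion of patients with any severe cough if the count is dichotomized. For a small count with many zeros, a median and IQR supply none of these. All patients receive dextromethorphan, alfentanil, BIS-guided propofol and topical lidocaine, so a low count is plausible, but the documents do not establish it.

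Two things are at stake. First, section 2.3 takes the sample-size step only if a difference is identified. Medians that coincide in spite of a real effect could lead the team to conclude that there is none. Second, if 21.1 is applied as written, nobody designing the later trial can recalculate its size on another endpoint scale, power or target effect.

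**Working it through.** **Inputs from the documents.** The outcome is a count (7.1). The planned summary is the median and IQR (8.3, 10.7). The arms are 24, 12 and 12, and 24 + 12 + 12 = 48, which agrees with "The estimated sample size within our institution is 48 patients". The 48 has no power basis, so there is no powered figure to reproduce. The topical arm of 24 faces 12 + 12 = 24 nebulizer patients when the two devices are pooled, or 12 for a single device.

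**Assumed inputs.** Negative binomial counts with mean m and dispersion k, so variance = m + m²/k; a true halving of the mean; two-sided alpha 0.05.

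**Step 1: one printed summary, several sample sizes.** Per arm at 90% power,

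n = (1.96 + 1.2816)² × [(1/m + 1/k) + (1/(0.5m) + 1/k)] / (ln 0.5)²,

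where (1.96 + 1.2816)² = 10.508 and (ln 0.5)² = 0.4805.

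| k | m | Quartiles | Variance | Bracket | n per arm |
|---|---|---|---|---|---|
| 2 | 0.55 | 0, 0, 1 | 0.70 | 6.455 | 142 |
| 1 | 0.6 | 0, 0, 1 | 0.96 | 7.000 | 154 |
| 0.5 | 0.7 | 0, 0, 1 | 1.68 | 8.286 | 182 |
| 0.3 | 1.0 | 0, 0, 1 | 4.33 | 9.667 | 212 |

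For the first row, 10.508 × 6.455 / 0.4805 = 141.2, rounded up to 142. All four rows print as 0 (0–1), yet the requirement differs by 212/142 = 1.5 times. That printed summary also allows an any-cough share from about 25% to 50%: a median of 0 needs at least half the patients at zero, and an upper quartile of 1 needs fewer than three quarters at zero.

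**Step 2: the same point at higher counts.** Constructed data with fixed summaries, 2 (1–3) in 24 patients and 1 (0–2) in 12, were given different upper tails. A two-sample comparison of means then needs 26 to 63 per arm at 80% power and 35 to 84 at 90%. At 80% power the ratio is 63/26 = 2.4.

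**Step 3: how often the medians hide a halving.** Simulation with 100,000 trials per row, k = 1, 24 against 24:

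| Spray mean | Medians equal | Median and both quartiles equal |
|---|---|---|
| 0.5 | 93% | 23% |
| 0.8 | 62–63% | 26% |
| 1.0 | 41% | 18% |
| 1.5 to 3 | 16–26% | 1–5% |

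With 24 against 12, medians are equal in about 91%, 59% and 39% of trials at means 0.5, 0.8 and 1.0. The median alone is therefore a weak signal at low counts. The full median-and-IQR line does better but still matches in about a fifth to a quarter of trials at means up to 1.0.

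**The case against.** A reader might infer that the promised sample size cannot be computed at all. The documents do not support that.

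- **Timing.** Section 21.1 takes effect only after completion. The principal investigator evaluates the data halfway and at completion (10.1) and is responsible for the primary data analysis (16.3), so patient-level records are in hand when the calculation would naturally be made. Section 2.3 does not place it later.
- **Context.** Section 21.1 sits under the banking heading and opens by marking the item as not applicable. It may mean only that no bank is created. The rules for trial data may be in the section 9 form, which cannot be seen here.
- **Summaries are not useless.** If the count were reported as any versus none, percentages would be enough: an assumed 50% against 25% needs 58 per arm at 80% power and 77 at 90%. Medians and IQRs give a rough figure. Section 8.3 does not forbid other calculations.

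A reader might also expect a table showing 0 (0–1) in every arm despite a large effect. That is possible but rare: about 2–5% of trials at 24/12/12 when both nebulizer arms are halved, across the low-count settings above (k = 1 at means 0.5, 0.8 and 1.0, and the four Step 1 pairs). In three of those four pairs, halving moves the population quartiles to 0 (0–0), so the IQR would show a change.

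These arguments remove the claim of impossibility, but part of the concern remains. The plan does not commit to an any-versus-none percentage, does not require the calculation before data disposal, and names no summary suited to its primary count.

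**Conclusion.** The concern holds as a weakness in the planned reporting, with a secondary ambiguity about retention. The study's purpose is not defeated. For a low cough count, the summaries in 8.3 and 10.7 leave the follow-on requirement undetermined, at roughly 142 to 212 per arm in the low-count examples. They can also show equal medians in about 41–93% of 24 against 24 trials at spray means of 0.5 to 1.0 when the true count is halved.

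These sizes rest on assumed means, dispersions, effect, alpha and power, because the documents give none. The equal-median problem shrinks to 16–26% at means of 1.5 to 3. The bar on later re-derivation depends on reading 21.1 literally and could be resolved by the section 9 form.

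**What to change.** **Section 8.3 (and 10.7).** Add: for the severe-cough count, report by arm the full frequency table, the mean, the variance and the percentage of patients with at least one severe cough, in addition to the median and IQR.

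**Section 21.1.** State that no bank for unspecified research is created, but that a de-identified, arm-coded patient-level dataset is kept for a fixed period consistent with the section 9 Research Data Plan form, and at least until the follow-on sample size has been determined. A fixed period avoids open-ended retention for a trial that is only conditional.

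**Cost.** A few table rows, matching IRB wording and a small storage duty. Enrollment, treatment and data collection do not change.

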21.2. Location of storage

Not applicable

21.3. Duration of storage

Not applicable

21.4. Access to data and/or specimens

Not applicable

21.5. Procedures to release data or specimens

Not applicable

